Sentinel node interrogation has yet to be fully evaluated in rectal cancer surgery due to technical limitations of obtaining SLNB from the mesorectum. As for breast cancer, rectal cancers can be excised by either radical or organ-preservation surgical techniques. Decision for either method is currently based on the risk of local recurrence or presence of lymph node metastasis. Radical surgery involves removal of the whole of the mesorectum and is associated with significantly worse functional outcome, morbidity and mortality. Current guidelines recommend that full thickness removal of the rectal tumour by transanal endoscopic microsurgery, TEM, is appropriate for small T1N0 cancers (less than 3 cm) where the risk of local recurrence (LR) is relatively low (NCCN guidelines, 2014). This surgery avoids removal of the whole mesorectum. The risk of LR increases with the depth of penetration of the rectal wall. Results from the UK TEM database show that the risk of LR at 36 months trebles when comparing T1N0 to T2N0 cancers of the same diameter (4.4% versus 14.3% respectively) (Bach et al, 2009). However, in 85% of rectal cancers that are T2N0 (based on tumours that are 2.1-3 cm diameter, with no lymphatic invasion) there is no LR at 36 months. There is a risk of subjecting patients to over-treatment in terms of surgery resulting in a significant risk of morbidity, mortality and impaired quality of life. On the other hand under-treatment of some “high risk” cancers would lead to recurrence. SLNB at TEM would potentially allow clinicians to excise T2 cancers in order to further stratify cancers based on future risk. This would avoid surgical over-treatment and under-treatment.

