## 5. OBJECTIVES AND OUTCOME MEASURES/ENDPOINTS

Objectives	Outcome Measures/Endpoints

Primary Objectives
 
Establish feasibility of identifying sentinel lymph node in rectal cancer:
 
[A] Adverse or hypersensitivity reactions after tracer injection in rectal cancer patients.
 
[B] Establish whether tracer is still present and detectable at the tumour injection site and in the lymph nodes at the time of surgery.
 
[C] Determine the impact of tracer injection on subsequent surgery (e.g. any difficulties due to discolouration or inflammation of tissue planes
	
[A] Frequency of adverse or hypersensitivity reaction.
 
[B] Frequency of tracer being detectable at the tumour injection site and in the lymph nodes at the time of surgery.
 
[C] Surgeon’s assessment of any difficulties encountered attributable to prior tracer injection

Secondary Objectives
 
[A] Correlate histopathology findings with tracer uptake in the lymph nodes.
 
[B] Radiologically evaluate the drainage pattern of tracer using a high resolution MRI, to establish a baseline for individual variation.
 
EX-VIVO part of study:
 
[C] Measure the distribution and spread of the tracer using the SentiMag hand-held probe in mesorectal specimen after rectal cancer surgery (in the pathology department). This is to establish a baseline in individual variation between specimens.
 
[D] Assess the accuracy of the SentiMag hand-held probe/ tracer in identifying "sentinel" lymph nodes. This will be determined in conjunction
	
[A] Correlation between histopathology findings and tracer uptake (determined by Sentimag probe) in the lymph nodes.
 
[B] High-resolution MRI mapping of the drainage pattern of tracer.
 
EX-VIVO part of the study:
 
[C] Mapping of the distribution of tracer in the mesorectal specimen using the SentiMag hand-held probe after rectal cancer surgery.
 
[D] Accuracy of the SentiMag hand-held probe/ tracer in identifying "sentinel" lymph nodes, determined by correlation with histopathology

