## 6. TRIAL DESIGN

This is a clinical study assessing the feasibility of detecting and sampling sentinel lymph nodes in rectal cancer patients using a magnetic nanoparticle tracer (Sienna+ or Magtrace, class IIa device, CE-approved in Europe). See Appendix A for a flow diagram of the study schema.

The study will be conducted in two phases. The first (ex-vivo) phase will assess the feasibility of detecting sentinel lymph nodes using tracer/SentiMag probe in patients undergoing radical surgery for rectal cancer. The second (in-vivo) phase will assess the feasibility of removing sentinel lymph nodes identified using tracer/SentiMag probe in patients undergoing less radical surgery for early rectal cancer.

Expected duration of patient participation is 2-3 weeks, from pre-operative tracer injection till discharge from hospital following rectal cancer surgery. Standard practice includes a pre-operative clinic visit for discussion, visit to the endoscopy unit for endoscopic assessment of the tumour pre-operatively and hospital admission for surgery. There will be one additional visit for an MRI scan. This will be performed on the same day as the endoscopy visit or on the day of surgery.

Screening of patients and provision of information about the study will occur during the pre-operative clinic visit. Consent will be taken on visit to the endoscopy unit and Sienna+ tracer will be injected during endoscopy. The Sentimag probe will be used during surgery and for second phase participants the sentinel lymph node will be removed. Pathological assessment of the removed specimen will be carried out after surgery. Patients will be monitored on the colorectal ward post-operatively until discharge.

During each stage data will initially be recorded in hard copy on CRF then transferred to a secure electronic record.

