## **8. TRIAL PROCEDURES**

Methodology training for investigators: At the start of the study, the principal investigators will undergo methodology training and practice the use of the hand held SentiMag probe device. The chief investigator will standardize the sentinel lymph node biopsy technique during this feasibility study.

Screening and preliminary discussion of research project with potential participant: During the standard pre-operative clinic visit patients who have been identified as potential participants will be screened and informed about the study by a clinician or colorectal specialist nurse. They will have an opportunity to ask questions and will be provided with an information sheet.

Informed consent: In the endoscopy unit a clinician will discuss the study further and take consent if the patient is willing to proceed. A letter will be sent to the participant's GP informing them of the study.

Endoscopic injection of tracer and post-injection monitoring: The magnetic tracer will be injected approximately 5 days before surgery during endoscopic assessment of the tumour. The rectal tumour

will be visualized by endoscopy, as per standard clinical practice. Up to 2ml tracer solution will be infiltrated systematically (in 4 quadrants) into the submucosa around the rectal tumour. After the procedure, patients will be monitored for 1 hour to ensure no hypersensitivity or adverse reactions occur and provided with a contact telephone number in case of any delayed reaction or side-effects on discharge.

MRI scan of pelvis: On the same day as the endoscopy unit visit or the day of surgery, patients will undergo an MRI scan of the pelvis. This will be done 2-3 hours after the endoscopic injection of tracer or on the day of surgery.

Rectal cancer surgery: Patients will undergo rectal cancer surgery according to their clinical indication. During surgery for the “ex-vivo” group, indocyanine green dye (ICG) will be injected near the tumour. At the conclusion of surgery the surgeon will make an assessment as to whether the tracer injection affected surgery, for example by causing inflammation in the tissue planes.

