## **12. STATISTICS**

### **12.1. Description of Statistical Methods**

All data will be stored in an Excel worksheet and analysed using Excel and R.

Frequency of event (adverse, hypersensitivity or complication) will equate to: number of adverse event/total number of recruited patients.

Frequency of tracer detection at surgery (at tumour site and in lymph nodes) will equate to: number of operations where tracer seen/ total number of operations on recruited patients.

Impact of tracer injection on subsequent surgery will be assessed by the surgeon's binary assessment as to whether surgery was more difficult than expected, and also free text comments to be analysed qualitatively.

A sentinel lymph node will be defined as the first lymph node draining the tumour and positivity defined according to the manufacturer's instructions. A "positive" node will be defined as having over 10% of the tracer activity of the site of initial submucosal injection. A "negative" node will be defined as having less than 10% of the tracer activity of the site of initial submucosal injection.

The detection rate for sentinel lymph nodes on MRI scan and Sentimag probe assessment will equate to: number of patients/specimens in whom a sentinel lymph node is identified/total number of examined patients/specimens.

MRI and Sentimag mapping will be qualitatively compared for all relevant patients/specimens (as appropriate) to establish a baseline of individual variability.

The presence and location of lymph nodes in the mesorectal specimen will be compared with the pathology findings for each patient in the ex-vivo part using correlation.

The success rate for removing the sentinel lymph node during TEM surgery will equate to: number of patients in whom the sentinel lymph node was removed/total number of patients undergoing TEM operation.

As this is a feasibility study, results will be continuously evaluated and adjustments made to the tracer dosage and timing of injection if indicated.

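### Primary endpoint B pools radical surgery and TEM in one detection rate, and primary endpoint C has no stated denominator or phase split

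*Combined protocol and SAP*

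**What the plan says.** **Endpoint B.** Section 12.1 introduces one measure, "Frequency of tracer detection at surgery (at tumour site and in lymph nodes) will equate to", and gives its formula as "number of operations where tracer seen/ total number of operations on recruited patients". Neither part refers to phase.

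**Endpoint C.** Section 5 lists it as "Surgeon’s assessment of any difficulties encountered attributable to prior tracer injection", outside both the ex-vivo and in-vivo headings. Section 8 adds the timing: "At the conclusion of surgery the surgeon will make an assessment as to whether the tracer injection affected surgery". Section 12.1 says it rests on the "surgeon's binary assessment as to whether surgery was more difficult than expected, and also free text comments to be analysed qualitatively". No numerator, denominator or phase is given.

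**The two groups.** Section 12.2 plans 20 radical-surgery patients and a further 20 TEM patients. Section 4 explains that "Radical surgery involves removal of the whole of the mesorectum" and that TEM avoids this. Section 6 describes the second phase as removing sentinel nodes "in patients undergoing less radical surgery for early rectal cancer". In section 8, specimen probing belongs to the first part only and intra-operative probing with node excision to the second part only. ICG is given only to the ex-vivo group.

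**What is phase-specific.** Secondary endpoints C and D are ex-vivo, and E is in-vivo. Section 12.1 gives node removal a TEM-only denominator, so the plan does restrict a denominator to one phase where it wants to.

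**The concern.** The two phases differ by design in operation, stage of disease, use of ICG and the setting in which nodes are probed. Finding tracer in a node of a resected specimen is not the same observation as finding it during an operation. A single ratio over both phases averages the two rates, with weights set by the recruitment targets. A satisfactory overall figure could then sit on top of a poor figure in one phase.

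Section 4 motivates the study by the possible value of sentinel node biopsy at TEM. A reader will therefore want to know how often tracer was detectable in TEM patients, and B as written does not report that. For C, the plan leaves open whether the difficulty ratings will be summarised over all patients, by phase, or only in narrative.

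**Working it through.** **Inputs.** Planned sizes of 20 and 20 (section 12.2), the total of 40 (Synopsis), and the formula for B (section 12.1). The documents give no expected rate, precision target, alpha or power (section 12.3 marks significance as not applicable). All event counts below are therefore assumptions chosen to show the mechanism.

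**1. The plan's own figure.** 20 + 20 = 40, which agrees with the Synopsis. No rate or precision is given from which 20 per phase could be derived.

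**2. What the pooled ratio estimates.** With x₁ detections in n₁ ex-vivo operations and x₂ in n₂ in-vivo operations:

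pooled B = (x₁ + x₂)/(n₁ + n₂) = [n₁/(n₁ + n₂)]·p₁ + [n₂/(n₁ + n₂)]·p₂

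At n₁ = n₂ = 20 this is (p₁ + p₂)/2, the plain mean of the two phase rates.

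**3. What one pooled value can contain.** Take x₁ + x₂ = 32, so pooled B = 32/40 = 80%. Neither count can exceed 20, so each lies between 32 − 20 = 12 and 20. Either phase could thus have a rate from 12/20 = 60% to 20/20 = 100%.

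**4. Intervals.** Exact (Clopper-Pearson) 95% limits: the lower is the 2.5% quantile of Beta(x, n − x + 1) and the upper is the 97.5% quantile of Beta(x + 1, n − x), with 0 and 1 at the extremes.

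| Illustration for B | Ex-vivo | In-vivo | Pooled |
|---|---|---|---|
| Equal rates | 16/20 = 80% (56% to 94%) | 16/20 = 80% (56% to 94%) | 32/40 = 80% (64% to 91%) |
| Unequal, wide gap | 20/20 = 100% (83% to 100%) | 12/20 = 60% (36% to 81%) | 32/40 = 80% (64% to 91%) |
| Unequal, smaller gap | 20/20 = 100% (83% to 100%) | 16/20 = 80% (56% to 94%) | 36/40 = 90% (76% to 97%) |

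The first two rows give the same pooled line, although the phases differ by 0 points in one and by 100 − 60 = 40 points in the other.

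**5. Endpoint C, only if it were pooled.** 0/20 (0% to 17%) and 6/20 = 30% (12% to 54%) would become 6/40 = 15% (6% to 30%). The plan does not say that this calculation will be made.

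**6. Cost of splitting.** At an observed 50%, the interval is 34% to 66% for 20/40 and 27% to 73% for 10/20. The width grows from about 32 to about 46 percentage points.

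**7. Should the phases be tested against each other?** With 20 per phase and two-sided 0.05, power is about 67% for true rates of 95% and 65%, and about 55% for 5% and 30% (assumed rates). A test could easily miss a large difference, so the comparison should stay descriptive.

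**The case against.** **The TEM rate is already reported through secondary E.** This stands in part. Section 5 defines E as TEM operations in which the node was identified by probe and then removed, and section 12.1 gives the removal rate a TEM-only denominator. In the 12/20 illustration, if the eight misses are nodal, probe-guided removal can reach at most 12/20, and that would be visible. But E does not cover the injection site, which is part of B, and says nothing about surgical difficulty. The section 12.1 formula counts removal alone, so a low value does not show whether tracer was absent or the node could not be taken out.

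**Pooling B has a rationale.** B asks whether tracer persists until surgery, and section 8 gives both phases the same injection method and approximate timing. For the injection site this is a fair argument, and it would be too strong to call the pooled rate meaningless. It is weaker for nodes, where the setting of the probing differs.

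**The probing settings may overlap.** Section 6 mentions probe use during surgery before singling out second-phase patients for node removal, which could mean intra-operative probing in both phases. Section 8 is more specific and assigns specimen probing to the first part and intra-operative probing to the second. The contrast drawn here rests on section 8.

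**Nothing forbids a by-phase table.** True. This is a small descriptive study of two separately recruited groups, and the authors may well report them side by side. The stated formula for B nevertheless does something else.

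**Stronger readings that the documents do not support.** A reader might infer that C, like B, is defined over all 40 operations. It has no denominator at all, so pooling is only one possible reading. A reader might also infer that the follow-on trial is specifically of node biopsy at TEM. Section 4 makes TEM the motivation but describes the next trial only as based on sentinel node biopsy in rectal cancer. Nor do the documents say how the probe gains access during TEM, or that tissue planes go largely undissected there. Section 8 in fact has a node dissected out in that group.

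**Conclusion.** The point holds in a limited form. For B, pooling is a stated rule: one ratio over all operations, covering two groups that differ by design. A pooled 80% is compatible with anything from 60% to 100% in either phase, assuming 20 operations in each. For C, the fault is an omission, since no denominator or phase split is specified. Secondary E reduces the masking for nodes in TEM patients but does not remove it.

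The size of any real masking is unknown, because it depends on a between-phase difference for which the documents give no expected value. If the phases perform alike, the pooled figure misleads nobody. This is a cheap improvement to the reporting. It does not call the design, the sample size or the conduct of the study into question.

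**What to change.** In section 12.1:

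- Make the by-phase rates the primary presentation of B and C. Use the number of operations actually performed in each phase as the denominator, planned as 20 each. Do not fix it at 20: section 8.7 excludes and replaces withdrawn patients while section 12.6 analyses everyone injected, so the counts may differ.
- State C's numerator and denominator: operations rated more difficult than expected, over operations performed in that phase. Keep the free text as planned.
- Give exact 95% confidence intervals for each rate. Present the phases descriptively, without a between-phase test.
- Keep the pooled total as a secondary line.

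This takes a sentence or two in section 12.1 and an extra table column. It uses data already to be collected and needs no further patients or procedures. The price is the wider per-phase intervals shown in the working.

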## 2. SYNOPSIS

Trial Title	Feasibility study of sentinel lymph node mapping in rectal cancer	
Internal ref. no. (or short title)	SentiRect Study	
Trial Design	Feasibility: proof of principle	
Trial Participants	Rectal cancer patients	
Planned Sample Size	40 patients	
Treatment duration	Single pre-operative administration	
Follow up duration	2-3 weeks	
Planned Trial Period	12 months	
	Objectives	Outcome Measures/Endpoints
Primary	
Establish feasibility of identifying sentinel lymph node in rectal cancer:
 
[A] Adverse or hypersensitivity reactions after Sienna+ tracer injection in rectal cancer patients.
 
[B] Establish whether tracer is still present and detectable at the tumour injection site and in the lymph nodes at the time of surgery.
 
[C] Determine the impact of Sienna+ injection on subsequent
	
[A] Frequency of adverse or hypersensitivity reaction.
 
[B] Frequency of tracer being detectable at the tumour injection site and in the lymph nodes at the time of surgery.
 
[C] Surgeon's assessment of any difficulties encountered

	surgery (e.g. any difficulties due to discolouration or inflammation of tissue planes)	attributable to prior Sienna+ injection.

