#### **12.6. Inclusion in Analysis**

All patients who receive the tracer injection will be included in the analysis.

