### **12.7. Procedures for Reporting any Deviation(s) from the Original Statistical Plan**

Not applicable. The analysis involves only simple statistical measures, and all proposed measures are necessary to determine feasibility.

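### The yes/no item that section 12.1 sets for primary endpoint [C] asks whether surgery was unexpectedly hard, not whether the tracer made it so

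*Combined protocol and SAP*

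**What the plan says.** Endpoint [C] is described in four places in the combined protocol and SAP.

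- **Section 2 (Synopsis), outcome [C]:** the surgeon's assessment of difficulties "attributable to prior Sienna+ injection".
- **Section 5, outcome [C]:** the surgeon's "assessment of any difficulties encountered attributable to prior tracer injection". The matching objective gives as its example "any difficulties due to discolouration or inflammation of tissue planes".
- **Section 8 (Trial Procedures):** at the end of the operation "the surgeon will make an assessment as to whether the tracer injection affected surgery".
- **Section 12.1:** the sentence opens "Impact of tracer injection on subsequent surgery will be assessed by the" surgeon's, and goes on to specify a "binary assessment as to whether surgery was more difficult than expected, and also free text comments to be analysed qualitatively".

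Section 12.1 gives a numerator and denominator for the frequency of adverse events and for tracer detection (endpoints [A] and [B]), but none for [C].

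**The concern.** Three of the four descriptions ask a causal question: did the tracer make this operation harder? The yes/no item in 12.1 asks something else: was the operation harder than the surgeon thought it would be? The first half of the 12.1 sentence states the target. The second half states what is recorded, and that part carries no attribution. The comments may supply a cause, but the plan neither requires one nor says that a comment can change the binary answer.

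[C] is one of three primary feasibility endpoints, and section 12.7 says that "all proposed measures are necessary to determine feasibility". Under section 12.6, "All patients who receive the tracer injection will be included in the analysis", so no untreated operations show how often surgery turns out harder than foreseen without the tracer. A positive answer to the literal item therefore cannot be read as tracer impact unless the comment behind it happens to name the tracer.

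**Working it through.** **Comparison of the texts**

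| Place | What the surgeon judges | Tracer named as cause? |
|---|---|---|
| Section 2, outcome [C] | difficulties due to the injection | yes |
| Section 5, outcome [C] | difficulties due to the injection | yes |
| Section 8 | whether the injection affected the operation | yes |
| Section 12.1, opening words | (states the target) tracer impact | yes |
| Section 12.1, binary item | whether surgery exceeded expected difficulty | no |
| Section 12.1, free text | not specified | not required |

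**How the literal item can go wrong**

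1. *Too many positives.* Any source of difficulty qualifies. The protocol itself adds some: section 8 gives ex-vivo patients an indocyanine green injection near the tumour during surgery, and has in-vivo patients undergo a probe search and node dissection after the tumour is out. Either could make an operation feel harder without being an effect of the pre-operative tracer.
2. *Too few positives.* Section 11.5 lists brown staining around the injection site as an expected reaction that may be visible at surgery. A surgeon who foresaw it could truthfully answer no, even if it caused trouble. The documents give nothing from which to size this.

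**Illustration of the first error**

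The documents state no rate, threshold or interval for [C], so there is no planned figure to reproduce. Inputs:

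- n = 40 (20 + 20, section 12.2).
- b = proportion of operations unexpectedly hard for non-tracer reasons. *Assumed*, at 5%, 10% and 20%.
- t = proportion with tracer-caused difficulty. *Assumed*, and independent of b.

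With no tracer effect (t = 0), expected positives = n × b and P(at least one) = 1 − (1 − b)^40:

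| b | Expected positives of 40 | P(at least one) |
|---|---|---|
| 5% | 40 × 0.05 = 2 | 0.871 |
| 10% | 40 × 0.10 = 4 | 0.985 |
| 20% | 40 × 0.20 = 8 | above 0.999 |

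An attributed item answered without error would give 0 of 40 in every row. Exact (Clopper-Pearson) 95% intervals:

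- 0/40: 0% to 1 − 0.025^(1/40) = 8.8%
- 4/40: 2.8% to 23.7%

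With a tracer effect of t = 5% (2 of 40), the literal item has rate 1 − (1 − b)(1 − t):

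- b = 5%: 1 − 0.95 × 0.95 = 9.75%, or 3.9 of 40
- b = 10%: 1 − 0.90 × 0.95 = 14.5%, or 5.8 of 40
- b = 20%: 1 − 0.80 × 0.95 = 24%, or 9.6 of 40

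**The case against.** The best defence is that 12.1 should be read as a whole. Its sentence introduces the item as the measure of tracer impact, and section 8 already says what the surgeon judges. No other surgeon assessment of difficulty is described, so 12.1 is naturally taken as shorthand for the section 8 judgement. The question actually put to surgeons is set by the case report form, which may ask about cause. With about 40 operations, someone can read the comment behind each positive answer. No test, threshold or decision rule depends on the count. A neutral question on difficulty followed by free text on cause is also a defensible design, and arguably less leading for an unblinded surgeon than a direct question about the tracer.

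Much of this stands. Attribution was clearly intended, the form cannot be checked, and nothing formal depends on the result. The 0 of 40 comparator assumes perfect attribution, so the contrast with 4 of 40 is the largest gain that rewording could bring at that assumed rate, not an expected one.

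It does not remove the mismatch. The opening words say what is to be learned, not what is recorded, and a surgeon answering the specified item can truthfully say yes for any reason. Reading the comments helps only where the surgeon chose to give a cause. The neutral two-step design would be sound if the plan said that the comment must state the cause and how it determines the count for [C]. It says neither.

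**Conclusion.** The concern holds, as a minor point. The binary measure in 12.1 does not match the endpoint that sections 2 and 5 define and section 8 describes. Followed literally, it mixes tracer and non-tracer difficulty and can miss tracer difficulty that was anticipated.

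Its size cannot be derived from the documents. At assumed background rates of 5% to 20% with no tracer effect, about 2 to 8 of 40 operations would be marked positive for reasons unrelated to the tracer. These figures show scale and are not evidence of bias in this study.

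The conclusion concerns the wording of 12.1 alone. It makes no claim about what surgeons have in fact been asked. The consequence is limited because [C] is reported descriptively, section 12.3 sets no significance level, and no threshold applies.

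**What to change.** Reword the 12.1 item in the terms of sections 5 and 8, for example: *Did the tracer injection cause any difficulty at surgery, such as staining of tissue or inflamed planes? Yes / No.* Report the number answering yes over the number of operations on injected patients, so that [C] has a stated denominator as [A] and [B] do. Overall difficulty against expectation can stay as a separate descriptive item, with the free text asked to give the cause. Then check that the case report form agrees.

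The cost is one sentence in 12.1 and, only if the form does not already ask about cause, one added question. No extra patients or visits are needed. There are two limits. For operations already done without an attribution question, the cause has to be read from the comments and may be missing. The reworded item also remains an unblinded opinion in a study without controls: the change aligns the measure with the endpoint but does not remove that weakness.
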